Number of subjects needed	72 patients
Planned study period	
Expected start date of inclusion: November 2012
 
Expected completion date of inclusion: April 2016
 
Primary endpoint analysis: April 2018
 
End of study: January 2019

EXAMINATION AND FOLLOW-UP SCHEDULE

	BEFORE TREATMENT	DURING EMBOLIZATION OR CHEMOEMBOLIZATION		DURING TREATMENT WITH EVEROLIMUS (24 months maximum)	AFTER STOPPING TREATMENT WITH EVEROLIMUS (after 24 months)
	Within 4 weeks prior to inclusion	Within 7 days prior to each embolization or chemoembolization	After embolization or chemoembolization	Every 3 months +/- 1 week	Every 3 months +/- 1 week
Informed consent	X				
CLINICAL EXAMINATION					
Weight, general condition WHO	X	X		X	X
Functional symptoms related to hormonal hypersecretion	X				
Medical and surgical history and treatments related to the endocrine tumor	X				
MORPHOLOGICAL EXAMINATION					
Triphasic thoracoabdomino-pelvic CT (to be performed in the investigating center, without injection, arterial time, portal time) *with measurement of liver metastases according to RECIST v1.1 criteria	X*		X**	X*	X***
ECG ± cardiological opinion if necessary	X				
BIOLOGICAL ASSESSMENT					
CBC/platelets, total and conjugated bilirubin, AST, ALT, PAL, creatinine, 24-hour proteinuria if treated with streptozotocin	X	X		X	
INR, TCA	X	X		X	
albumin, urea, blood ionogram, GGT	X			X	
Serum cholesterol and triglycerides, fasting blood glucose and HbA1c	X			X	
Chromogranin A, urinary 5HIAA	X			X	
B viral serology (HBV-DNA, HBsAg, anti-HBsAb, anti-HBcAb) and C****	X			****	
Pregnancy test for women of childbearing age	X (within 7 days of starting treatment)				

*With target measurement according to RECIST v1.1 criteria

**To be performed for technical reasons only. Measurements should not be used for evaluation of tumor response

*** If everolimus is discontinued for reasons other than hepatic progression, continue morphological monitoring until hepatic progression occurs

**** In case of B and C viral serology, follow up the DNA and RNA load respectively every 3 to 6 weeks (see table 2-2 and 2-3)

I. OBJECTIVES OF THE TRIAL

1. Main objective

The primary objective of the study is to determine whether treatment with everolimus for 24 months prolongs progression-free survival according to RECIST 1.1 criteria. The primary endpoint will be progression-free survival at 24 months in patients receiving hepatic embolization or chemoembolization followed by everolimus therapy.

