- Clinical assessment: weight, general condition (WHO)
- Evaluation of the tolerance of the previous embolization or chemoembolization
- Biological check-up:
 - CBC-platelets
 - INR, aPTT, creatinine, bilirubin (total, conjugated), AST, ALT, PAL

NB: An abdominal CT scan may be performed if necessary for technical reasons before the 2nd embolization or chemoembolization session. Caution: this imaging should not be used to evaluate the response to treatment of metastases.

Every 3 months (+/- 1 week) from the date of the first embolization or chemoembolization (except DNA and ARC monitoring for positive serology)

- Clinical assessment: WHO, weight, evaluation of side effects
- Bioassay:
 - CBC/platelets, urea and creatinine + calculated creatinine clearance (Cockcroft formula), blood ionogram
 - INR, aPTT, albumin, alkaline phosphatase, AST, ALT, bilirubin (total and conjugated), gamma-GT
 - Serum cholesterol and triglycerides
 - Fasting blood glucose and HbA1c
 - Chromogranin A, urinary 5HIAA
- If HBV positive, monitor DNA approximately every 3 weeks or 6 weeks depending on the result (see Table 2-2)

- If HCV positive, monitor RNA every 6 weeks (see Table 2.3)
- Morphological assessment: triphasic thoracic-abdominal-pelvic CT scan with target measurement according to RECIST V1.1 criteria (Appendix 3). Evaluation CT scans should be performed in the same center as the initial examination

NOTE: Patients whose treatment is temporarily or permanently discontinued due to an adverse event or laboratory abnormality suspected to be related to everolimus should be monitored at least weekly until the adverse event resolves or returns to Grade 1

2. Post-treatment monitoring protocol

- **After discontinuation of treatment for hepatic progression**
 - After hepatic progression, the clinical, biological and morphological monitoring of the patient will be left to the investigator's discretion
- **After discontinuation of treatment for a reason other than hepatic progression**
(e.g. toxicity, extra-hepatic progression, patient's wish, :)
 - Morphological surveillance: CT every 3 months until liver progression occurs, according to the same modalities as the initial morphological evaluation (triphasic thoraco-abdomino-pelvic CT with target measurement according to RECIST V1.1 annex 3)

IX. STOP PROCESSING THE STUDY

The processing of the study will be stopped in case of:

- Investigator's decision

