- Major toxicity requiring discontinuation of treatment (despite protocol adaptations)
- Serious or unexpected event requiring discontinuation of protocol treatment
- Disease progression (hepatic, extra-hepatic, clinical)
- Patient refusal
- Death of the patient

X. CENTRALIZED PROOFREADING OF TDM

To address the primary endpoint of efficacy of everolimus treatment after embolization or chemoembolization, a centralized review of morphological examinations of the inclusion workup and follow-ups will be performed by an independent review committee.

To do this, make a copy of the imaging to be kept in the patient's file. The FFCD CRA in charge of your center will make an anonymized copy of the CD ROM and send the imaging to the FFCD imaging platform.

XI. MANAGEMENT OF SERIOUS ADVERSE EVENTS (SIA)

Security assessment parameters

Safety will be assessed by evaluating the general and clinical condition of the patients and by collecting events occurring between visits during consultations, by regular blood tests. Toxicities will be assessed using the NCI-CTC-AE version 4.0 toxicity scale (see Appendix 4).

Definitions

a. Adverse Event (AE)

An adverse event is a harmful occurrence in a person who is a subject of biomedical research, whether or not the occurrence is related to the research or the product being investigated.

All adverse events will be recorded in the observation book on the pages provided.

b. Serious Adverse Event (SAE)

A serious adverse event is any event that

- Resulting in death,
- Life-threatening,
- Leading to hospitalization or prolonged hospitalization,
- Causing permanent disability or severe temporary incapacity,
- Causing a birth defect, fetal malformation or abortion,
- Medically significant

The terms disability and incapacity correspond to any temporary or permanent physical or psychological handicap, clinically significant and affecting the physical activity and/or quality of life of the patient.

Any clinical event or laboratory result considered serious by the investigator and not corresponding to the severity criteria defined above is considered medically significant. They may put the patient at risk and require medical intervention to prevent an outcome corresponding to one of the above mentioned severity criteria (e.g. overdose, second cancers, pregnancies and new events may be considered as medically significant).

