5.7 Judging criteria

5.7.1 Main criterion

The primary endpoint is the rate of living patients without liver progression 24 months after inclusion. Hepatic progression is defined according to RECIST V1.1 criteria and is based on centralized review (or on the investigator's opinion in case of impossible review).

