5.7.2 Secondary endpoints of effectiveness

5.7.2.1 Rate of living patients without liver progression in mRECIST at 24 months

The rate of living patients without liver progression 24 months after inclusion will also be described according to mRECIST criteria and based on centralized review.

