5.7.2.2 Survival without liver progression

It is defined as the time from the date of inclusion to the date of first hepatic progression (based on centralized review or on the investigator's opinion in case of impossible review) or the date of death (regardless of cause). Living patients without hepatic progression will be censored at the point date or the date of last morphological evaluation.

Live patients for whom no morphological evaluation is available will be censored at inclusion date + 1 day.

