6.1.2 Population of analysis for primary endpoint (PC)

The analysis population for the primary endpoint is defined as the ITT population of evaluable patients. A patient is considered evaluable if he or she has received at least one dose of everolimus and at least one treatment-related imaging.

A patient who dies (from any cause after treatment) or progresses in liver function before 24 months is evaluable and considered a failure for the primary endpoint.

Patients without a 24-month evaluation will be reviewed according to the following rules:

- If the patient has a later assessment (27 months or more) and is not progressing at that time, then they will be considered progression-free at 24 months
- The other patients will be reviewed at a medical review to decide, in view of the patient's entire file, whether they can be considered as failed or as truly non-evaluable (a rate of 5% of additional patients has been planned for these situations).

A listing of patients excluded from the CP population will be provided with the reasons for their exclusion.

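### Required CT ends at locally called hepatic progression, but the primary endpoint is read centrally, so a patient whose local progression is not confirmed can be declared non-evaluable instead of counted as a failure

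*Protocol*

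**What the plan says.** **When required imaging ends.** Under Protocol VIII.2, "After hepatic progression, the clinical, biological and morphological monitoring of the patient will be left to the" investigator's discretion. If treatment stopped for another reason, the same section requires "CT every 3 months until liver progression occurs". The footnote to the examination schedule agrees: "If everolimus is discontinued for reasons other than hepatic progression, continue morphological monitoring until hepatic progression occurs". Protocol IX lists progression as a reason to stop study treatment and mentions no central confirmation. Protocol X describes copying scans for an independent review committee, and describes no reading step before treatment or imaging stops.

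**Who judges the endpoint.** SAP 5.7.1 defines the primary endpoint as alive without liver progression 24 months after inclusion; hepatic progression "is based on centralized review (or on the investigator's opinion in case of impossible review"). Protocol XII.2 has the same hierarchy.

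**What happens without a 24-month evaluation.** SAP 6.1.2 first calls a patient evaluable after one everolimus dose and one imaging, and makes death or liver progression before 24 months a failure. It then adds rules for patients lacking a 24-month evaluation. A scan at 27 months or later without progression makes the patient a success. For the rest, "The other patients will be reviewed at a medical review to decide" between failure and truly non-evaluable, on the whole file.

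**Secondary analyses.** For liver PFS, SAP 5.7.2.2 says "Living patients without hepatic progression will be censored at the point date or the date of last morphological evaluation". The mRECIST rate (SAP 5.7.2.1) "will also be described according to mRECIST criteria and based on centralized review".

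**The concern.** Two different readers control two linked things. The local reader in effect decides when required scanning ends, and the central reader decides whether the endpoint has occurred. When they disagree on a readable scan, review was possible, so the investigator's call does not count as progression. Yet nothing now obliges anyone to obtain the scan that would settle the 24-month status.

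The missing status then follows from a clinician's judgement that the patient was failing. Whether the patient stays in the denominator is decided case by case in an open-label trial, with no stated criteria beyond the file. A rule that allows exclusion on grounds related to outcome matters most when the result lies close to the decision limit, and the limit here is one count in a single arm of 68.

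**Working it through.** **1. Tracing the patient through the rules.** Local hepatic progression is called at, say, month 9; central review reads the scan and does not confirm it; the patient is alive with no scan at or after 24 months.

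| Rule | Result |
|---|---|
| Protocol VIII.2 | no further CT required |
| SAP 5.7.1 | review possible, so the local call is not used |
| SAP 6.1.2, automatic failure | not met: no death, no centrally read progression |
| SAP 6.1.2, scan at 27 months or later | not met |
| SAP 6.1.2, medical review | failure or non-evaluable |
| SAP 5.7.2.2 | censored at the last scan |

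**2. Reproducing the design.** Inputs from SAP 5.5 and 5.6.1: p0 = 0.35, p1 = 0.50, one-sided alpha 5%, power 80%, n = 68, success if at least 31.
- Alpha = P(X ≥ 31 | 68, 0.35) = 0.0461.
- Power = P(X ≥ 31 | 68, 0.50) = 0.8019.
- Allowance: 68/0.95 = 71.6, rounded up to 72.

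The plan's figures reproduce.

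**3. What a few exclusions do near the limit.** The SAP states a count only for 68 evaluable patients. For other denominators I use the exact one-sided p-value P(X ≥ x | n, 0.35) and the exact one-sided 95% lower bound, in line with SAP 7.4.

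| Handling | Rate | p | Lower bound | Result |
|---|---|---|---|---|
| 3 counted as failures | 30/68 = 44.1% | 0.075 | 33.8% | fails |
| same 3 excluded | 30/65 = 46.2% | 0.041 | 35.5% | passes |
| 4 counted as failures | 31/72 = 43.1% | 0.096 | 33.1% | fails |
| same 4 excluded | 31/68 = 45.6% | 0.046 | 35.2% | passes |

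Four patients is the whole planned allowance (72 − 68 = 4).

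**4. Type I error under assumed frequencies.** Let d be the share of patients with unconfirmed local progression, all of them excluded, and f the share of these who would truly fail by 24 months. Neither is given in the documents. With a true rate of 35% in 72 patients, the success rate among those left is s = (0.35 − d(1 − f))/(1 − d). For d = 5% and f = 100%, s = 0.35/0.95 = 0.368. Resetting the exact critical value to the number evaluable and averaging over that number gives:

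| d | f = 65% | f = 80% | f = 100% |
|---|---|---|---|
| 0 | 0.037 | 0.037 | 0.037 |
| 5% | 0.038 | 0.051 | 0.073 |
| 10% | 0.037 | 0.067 | 0.131 |

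The column f = 65% is the average failure risk under H0 (1 − 0.35). There the error does not move: inflation needs higher-than-average risk.

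**The case against.** The case against has substance.

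- **Loss is not automatic.** Death before 24 months is a failure, a discretionary scan may exist, and the medical review can return failure. A local progression call in the file would point that way. A reader might infer that these patients necessarily drop out of the primary analysis; the SAP says only that they may. What stands is that the SAP does not settle it in advance.
- **Impossible review could be read broadly**, to cover an absent 24-month scan, so that the investigator's opinion takes over. The text does not say this, and the scan in dispute was reviewable.
- **Absence of real-time central reading is inferred** from silence in Protocol X. That is fair, but no passage makes the end of imaging depend on central agreement.
- **Direction of bias is assumed.** At average risk, excluding these patients does no harm, as step 4 shows.
- **Size cannot be borrowed.** A reader might take the 12.0-month (centre) and 16.4-month (central) median PFS in the everolimus arm of the phase III trial cited in Protocol XIII and derive a number of discordant patients. Those medians cover progression at any site, in patients treated with octreotide and everolimus in a different setting. A gap between medians also mixes disagreement on dates with disagreement on status. It does not count patients with unconfirmed hepatic progression.
- **Censoring touches only a secondary analysis.** The SAP primary analysis is a binomial proportion (SAP 7.4).

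**Conclusion.** The gap is real and lies in the stated rules, not merely in missing detail. Required CT ends on what is in practice a local call, the endpoint follows a central one, and the patient caught between them can be excluded after the fact or censored at the last scan. The documents do not show how many patients this concerns, nor that they fail more often than others. The upward bias is therefore conditional on that second point, which is plausible because the investigator judged them to be progressing.

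Under that condition, three or four exclusions suffice to change the conclusion when the result is near the limit. Type I error would rise from 0.037 to between 0.051 and 0.073 if 5% of patients are affected and all are excluded, assuming that 80 to 100% of them would fail by 24 months. Far from the limit, the effect on the conclusion is small. The point deserves a change to the SAP before database freeze; it does not show that the trial's result will be wrong.

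**What to change.** Before database freeze, as SAP 7.1.2 allows:

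1. **SAP 5.7.1 and 6.1.2.** State that investigator-assessed hepatic progression before 24 months that central review does not confirm, with no later imaging showing absence of hepatic progression at or after 24 months, is a failure and is not non-evaluable.
2. **SAP 5.7.2.2 and 7.5.2.** Add a supportive liver-PFS analysis that takes the local progression date as the event.
3. **Reporting.** Tabulate local against central agreement on hepatic progression. Send to central review any CT already done after the local call, up to 24 months.
4. **mRECIST rate.** Do not impose the failure rule here. It would turn RECIST progressors without later CT into mRECIST failures and erase the contrast this descriptive endpoint exists to show. Report how many patients lack a 24-month mRECIST status, and give the rate with them counted both ways.

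The cost is SAP wording, two tables and the transfer of existing scans; no added patient procedure is needed. The downside is a somewhat more conservative primary rate, since some patients counted as failures may in truth have been free of hepatic progression at 24 months.

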Everolimus will be started 7 days after embolization or chemoembolization or when liver toxicities have returned to a grade ≤ 1 according to the NCI CTIC version 4.0 toxicity scale. Treatment should not be initiated beyond 30 days after embolization or chemoembolization.

If embolization or chemoembolization cannot be performed after patient inclusion, everolimus MUST NOT be started.

If embolization or chemoembolization is postponed, wait for embolization or chemoembolization to start everolimus as described above. If embolization or chemoembolization is definitely cancelled, DO NOT ADMINISTER everolimus and follow the patient according to the recommendations (see paragraph VIII-2: monitoring after cessation of treatment).

For the second session, everolimus will be stopped the day before the session and restarted in the same manner as initially, i.e., 7 days after embolization or chemoembolization or when liver toxicities have returned to a grade ≤ 1 according to the NCI CTIC toxicity scale version 4.0 and within a maximum of 30 days after embolization or chemoembolization.

Method of administration

Everolimus should be taken orally once a day at the same time each day, with or without food. The tablets should be swallowed whole with a glass of water. The tablets should not be chewed or crushed.

If a dose is missed, the patient should not take an additional dose, but should take the next prescribed dose.

3- Concomitant treatments to be avoided

Everolimus is a substrate of CYP3A4 and a moderate inhibitor of P-glycoprotein (PgP). Therefore, the absorption and subsequent elimination of everolimus may be influenced by drugs that act on CYP3A4 and/or PgP. In vitro, everolimus is a competitive inhibitor of CYP3A4 and a mixed inhibitor of CYP2D6.

Known and theoretical interactions with selective inhibitors and inducers of CYP3A4 and PgP are described in the Table below.

CYP3A4 and PgP inhibitors that may increase everolimus concentrations: CYP3A4 or PgP inhibitors may increase blood levels of everolimus by decreasing the metabolism or efflux of everolimus from intestinal cells.

CYP3A4 and PgP inducers that may decrease everolimus concentrations: Substances that are CYP3A4 and PgP inducers may decrease blood levels by increasing everolimus metabolism or efflux of everolimus from intestinal cells.

Effect of other active substances on everolimus

Active substances by interaction	Recommendations for Concomitant Administration
Potent CYP3/PgPA INHIBITORS	

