Grade 2 (except pneumonia - see Table 1-4)	If toxicity is tolerable to the patient, maintain the same dose. In case of intolerable toxicity for the patient, discontinue everolimus until recovery to grade ≤ 1 . Then reintroduce everolimus at the same dose. If an event returns to grade 2, discontinue everolimus until recovery to grade ≤ 1 . Then reintroduce everolimus at the lower dose level.
Grade 3 (except hyperlipidemia*) (except pneumonia - see Table 1-4)	Interrupt everolimus until recovery to grade ≤ 1 . Then reintroduce everolimus at the lower dose level. For pneumonia, consider short-term steroid therapy.
Grade 4	Stopping everolimus
Any non-hematologic toxicity requiring interruption for a period ≥ 3 weeks	Stopping everolimus

*Grade 3 hyperlipidemia (hypercholesterolemia and/or hypertriglyceridemia) should be managed with medical treatments.

Table 1-2

HEMATOLOGICAL Toxicity (NCI-CTC V4.0)	Grade	Actions
Thrombocytopenia	Grade 2 (platelets $< 75, \geq 50 \times 10^9 /l$)	Interrupt everolimus until recovery to grade ≤ 1 ($\geq 75 \times 10^9 /l$). Then reintroduce everolimus at the initial dose. If thrombocytopenia returns to grade 2, discontinue everolimus until recovery to grade ≤ 1 . Then reintroduce everolimus at the lower dose level.
	Grade 3 (platelets $< 50, \geq 25 \times 10^9 /l$)	Interrupt everolimus until recovery to grade ≤ 1 (platelets $\geq 75 \times 10^9 /l$). Then resume everolimus at a lower dose level.

		If thrombocytopenia recurs at grade 2, discontinue everolimus.
	Grade 4 (platelets < 25×10^9 /L)	Stopping everolimus
Neutropenia	Grade 3 (neutrophils < 1, $\geq 0.5 \times 10^9$ /L)	Interrupt everolimus until recovery to grade ≤ 1 (neutrophils $\geq 1.5 \times 10^9$ /L). Then resume everolimus at the initial dose. If PNN returns to grade 3, withhold everolimus until PNN is $\geq 1.5 \times 10^9$ /L. Then resume everolimus at the lower dose level. Discontinue study treatment if a third episode of Grade 3 neutropenia occurs
	Grade 4 (neutrophils < 0.5×10^9 /L)	Interrupt everolimus until recovery to grade ≤ 1 (neutrophils $\geq 1.5 \times 10^9$ /L). Then resume everolimus at the lower dose level. If Grade 3 or 4 neutropenia occurs despite this dose reduction, discontinue everolimus

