Hypersensitivity reactions with symptoms including anaphylaxis, dyspnea, flushing, chest pain, or angioedema (e.g., swelling (edema) of the airways or tongue, with or without respiratory failure) have been observed with everolimus.

Hyperglycemia has been reported in clinical trials. It is recommended that fasting blood glucose be monitored prior to initiation of everolimus therapy and periodically thereafter. Optimal glycemic control should be achieved prior to initiating everolimus therapy in a patient. Mouth ulcers, stomatitis and oral mucositis have been observed in patients treated with everolimus. In these cases, topical treatments are recommended, but alcohol or hydrogen peroxide mouthwashes should be avoided.

Elevations in serum creatinine, usually mild, have been reported in clinical trials. It is recommended that renal function be monitored before starting everolimus therapy and periodically thereafter.

Decreases in hemoglobin, lymphocytes, platelets and neutrophils have been reported in clinical

trials. It is recommended that complete blood counts be monitored prior to the initiation of everolimus therapy and periodically thereafter.

The use of live vaccines and close contact with individuals who have received live vaccines should be avoided during treatment with everolimus.

Hypophosphatemia, hypomagnesemia, hyponatremia and hypocalcemia have been reported.

c. Management of stomatitis/oral mucositis/aphthae

Oral stomatitis/mucositis/ mouth ulcers due to everolimus should be treated with local symptomatic therapy. It should be noted that investigators in previous trials have described oral toxicities associated with everolimus in terms of mouth ulcers rather than mucositis or stomatitis. If your examination reveals canker sores rather than more general inflammation of the mouth, please classify the adverse event as such. Please follow the template below for treatment of oral stomatitis/mucitis/aphthas:

1. For mild toxicity (Grade 1), use conservative measures such as **alcohol-free mouthwash or salt water mouthwash (0.9%)** several times a day until resolved.

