Overall survival will be defined as the time interval between the date of inclusion and the date of death regardless of the cause of death or the date of last news for living patients.

Tolerance to treatment will be assessed by:

- duration of treatment, doses received, dose reductions and deferrals
- Toxicities collected at each monthly visit, and described according to NCI-CTC version 4.0 criteria; Grade 3, Grade 4 and Grade 5 toxicities will be reviewed.
- the number and description of SAEs
- the evolution of the WHO performance index.

Calculation of the number of subjects needed

According to the literature, the median progression-free survival after embolization or chemoembolization ranges from 15 to 19 months with a progression-free survival rate of approximately 35%. As there is no information on progression-free survival in the literature, the hypotheses were built on the progression-free survival data.

The assumptions used to calculate the number of subjects are as follows:

H0: a 24-month progression-free survival rate of less than 35% is not acceptable

H1: A 24-month liver progression-free survival rate greater than 35% would demonstrate the utility of everolimus therapy with an expected 24-month liver progression-free survival rate of 50%,

To obtain a power of 80% with a first-species risk of 5% (one-sided), it is required to include 68 patients according to the assumptions established above (using the exact binomial distribution).

Taking into account a rate of lost to follow-up or patients not evaluable for any reason except death, 72 patients will be included.

3. Statistical analysis plan

Populations of analysis

Patients included in the study will be described (ITT) as well as patients not evaluable for the primary endpoint.

A patient is considered evaluable if he or she has received at least one dose of everolimus and one evaluation.

All efficacy analyses will be performed on a modified intention-to-treat basis (evaluable patients) included in the study regardless of eligibility criteria and treatment received.

Tolerability population: the ITT population that received at least one dose of the treatments.

In all cases of discontinuation, the patient remains in the intention-to-treat analysis. There is no exclusion period for a subsequent therapeutic trial.

Main analyses

A statistical analysis plan will be written prior to freezing the database.

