The description of clinical and medical variables will be done using percentages (95% confidence interval) and mean (standard deviation) and median (Min-Max) as well as the interquartile range (Q1-Q3).

Survivals and times will be estimated by the Kaplan Meier (KM) method. They will be described by medians and rates at different time points with their 95% confidence intervals. Median follow-up time will be calculated using the reverse Kaplan Meir method.

The results for the primary endpoint will also be described by a Water Fall plot representing for each patient the percentage change at 24 months in liver metastasis size since the measurement at inclusion according to the response according to the RECIST V1.1 criteria.

The time to onset of grade 3/4/5 toxicity will be estimated using the Kaplan Meier method.

Exploratory analyses

- research into factors predictive of progression-free survival and/or overall survival
- comparison of progression-free survival between embolization alone and chemoembolization

4. Independent committees

An independent committee will be formed and will include at least: two physicians (oncogastroenterologists), a statistician, a pharmacovigilance expert. The independent committee may meet at any time during the protocol when deemed necessary by the Sponsor.

XIII. JUSTIFICATION OF THE TEST

Neuroendocrine tumors (NETs) are a heterogeneous group of rare tumors. The prevalence of these tumors is estimated to be between 0.4 and 1 per 100,000 inhabitants per year. In the gastrointestinal tract, the most frequent locations are the appendix (19%), the small intestine (15%) and the rectum (11%). Neuroendocrine tumors of the small intestine mainly affect young adults between 30 and 35 years of age, while those of the colon tend to occur around 60 years of age [[1]].

Treatment of digestive endocrine tumors

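### Toxicity is collected monthly in the tolerance text but every 3 months in the visible schedule; the schedule leaves silent laboratory toxicity unchecked for long stretches, and the SAP omits the planned time-to-toxicity analysis

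*Protocol*

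**What the plan says.** **Interval.** Protocol XII.2, under the secondary criteria, assesses tolerance through "Toxicities collected at each monthly visit". Section VIII.1 places the evaluation of side effects and the blood work at visits "Every 3 months (+/- 1 week) from the date of the first embolization or chemoembolization". The examination and follow-up schedule uses the same 3-monthly column during everolimus for "CBC/platelets, total and conjugated bilirubin, AST, ALT, PAL, creatinine". The only other scheduled routine blood work after inclusion is the check in the 7 days before each session.

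**Rules that need a blood result.** Table 1-2 acts on platelets at grades 2, 3 and 4 and on neutrophils at grades 3 and 4. Table 1-3 acts on hemoglobin at grades 3 and 4. An example is "If thrombocytopenia returns to grade 2, discontinue everolimus until recovery to grade" 1 or lower. Section VI.2 lets everolimus start on day 7 or "when liver toxicities have returned to a grade" of at most 1, and no later than day 30.

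**General monitoring text.** Section VII.2.b says "It is recommended that complete blood counts be monitored prior to the initiation of everolimus therapy and periodically thereafter". Section XI speaks of "collecting events occurring between visits during consultations, by regular blood tests". Neither gives an interval. Weekly monitoring (VII.2 and VIII.1) applies once everolimus has been interrupted or stopped for a suspected toxicity.

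**Analysis.** Protocol XII.3 states: "The time to onset of grade 3/4/5 toxicity will be estimated using the Kaplan Meier method". SAP 7.6.4 lists only tables of maximum grade per patient.

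**The concern.** The two intervals cannot both be followed. A site working from the schedule table departs from the tolerance definition in XII.2. A site working from XII.2 finds no visit in the visible schedule at which to collect the data.

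The interval also matters for dosing. A rule triggered by a blood count can act only if a count is taken. Section VII.2.b lists anemia, thrombocytopenia and neutropenia among the common grade 3-4 events of everolimus, so these rules are expected to be used. If the 3-monthly text governs, a patient without symptoms could meet a rule to interrupt or stop and stay on an unadjusted dose until the next visit.

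For the analysis, a silent laboratory event would carry the date of the visit that found it rather than its onset date. The Kaplan-Meier estimate in XII.3 depends on onset dates, and the SAP gives that analysis no population, time origin or dating rule.

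**Working it through.** The plan gives no figure for this point, so there is none to reproduce. The calculation is calendar arithmetic on the plan's own inputs.

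**Inputs**
- 1 month = 30.4375 days (SAP 7.1.3).
- Visits every 3 months, plus or minus 7 days, from the first session (Protocol VIII.1).
- Everolimus starts on day 7 by default and on day 30 at the latest (Protocol VI.2).
- One or two sessions, 4 to 8 weeks apart (SAP 5.2); blood check within 7 days before each (Protocol VIII.1).
- Everolimus for up to 24 months (Protocol VI.2).

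**Month-3 visit.** 3 x 30.4375 = 91.3 days after the first session. With the window this is 84.3 to 98.3 days.

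**One-session patient: days on everolimus before the first scheduled count** (visit day minus start day)

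| Start | Earliest visit | Latest visit | Weeks |
|---|---|---|---|
| Day 7 | 84.3 - 7 = 77.3 | 98.3 - 7 = 91.3 | 11.0 to 13.0 |
| Day 30 | 84.3 - 30 = 54.3 | 98.3 - 30 = 68.3 | 7.8 to 9.8 |

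**Two-session patient, day-7 start.** The second session falls on day 28 to 56 and its blood check on day 21 to 56. Subtracting 7 gives 14 to 49 days on drug.

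**Later gaps between 3-monthly visits.** 91.3 days, minus or plus 14 when adjacent windows move in opposite directions, gives 77.3 to 105.3 days, or 11.0 to 15.0 weeks.

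**Number of checks over 24 months.** 24/3 = 8 on the 3-monthly text and 24/1 = 24 on the monthly text, a difference of 16.

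**Does other text close the gap?**
- Weekly monitoring follows an interruption or stop, so it cannot detect the event that should cause one.
- The statements in VII.2.b and XI set no interval.
- HBV- and HCV-positive patients have viral-load tests about every 3 or 6 weeks, but these are not blood counts.
- Section XI allows events between visits to be collected at consultations. That works for events the patient notices, but not for a silent fall in platelets or neutrophils.

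**Protocol against SAP.** XII.3 plans a time-to-onset estimate for grade 3/4/5 toxicity. SAP 7.6.4 contains four maximum-grade tabulations and no time-to-event analysis, and the SAP does not say that it was dropped. This difference exists whichever interval applies.

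**The case against.** The strongest reply is that this is a wording conflict in descriptive safety collection and that ordinary care fills the gap. Much of that stands. Symptomatic events and SAEs are captured whatever the interval, sites may test more often, and two-session patients have an extra check. Bilobar disease is treated one lobe per session, so two sessions may be common; the documents do not give the one-session share. The treatment-scheme and sequence figures are not shown, and the product characteristics in Appendix 6 are not available, so a monthly visit or test interval may be stated there. Table 1-4 refers to cycles, which the visible text does not define.

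Three stronger readings are tempting, but the documents do not support them.

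- *Every patient goes 11-13 weeks without a scheduled count.* That range holds only for one session with a day-7 start. A later start or a second session shortens it.
- *The planned Kaplan-Meier curve will sit at zero until month 3.* XII.3 plans one curve for all grade 3/4/5 toxicity. Stomatitis, infections, diarrhea, fatigue and pneumonitis are among the common severe events and can be dated between visits. Only the silent laboratory part is shifted to visit dates. The documents give no early rate for it, so no size of bias can be stated.
- *Everolimus may be started or restarted without a liver check.* The grade condition in VI.2 already obliges the investigator to check before a delayed start or a restart. What is missing is a line in the schedule.

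The reply does not remove the contradiction itself, or the fact that the visible schedule sets no timed count to support the count-triggered dose rules early on everolimus.

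**Conclusion.** The concern holds in limited form. The visible documents give two incompatible intervals for collecting toxicity and do not show which was intended. If the 3-monthly text governs, the first scheduled count comes after 77-91 days on drug (one session, day-7 start) or 54-68 days (one session, day-30 start), and later gaps run 11-15 weeks. If the monthly text governs, sites following the schedule would make about 8 of 24 intended collections. The loss concerns silent laboratory toxicity, which would be acted on late and dated late. The absence of the time-to-toxicity analysis from the SAP is a separate and definite omission.

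The day counts assume that visits fall within their windows and that no unscheduled tests are done; they need no assumed event rate. The maximum-grade tables, primary endpoint, sample size and decision rule can be run as planned. This is worth correcting but does not threaten the trial's main conclusion. Confidence is medium, because the missing figures and appendix could settle the interval.

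**What to change.** 1. **State one interval.** Preferably, bring the schedule table and VIII.1 into line with XII.2 by adding a monthly side-effect and blood check during everolimus: CBC with platelets, creatinine, bilirubin, AST and ALT.
2. **If 3-monthly visits are intended,** correct XII.2 and add the same check at least at months 1 and 2 after the first session; a pre-session check in that window counts. At nominal dates the first on-drug count then falls at 30.4 - 7 = 23.4 days for a day-7 start and at 60.9 - 30 = 30.9 days for a day-30 start. This is a minimum, because the later 11-15 week gaps remain.
3. **List in the schedule** the liver test that VI.2 already implies before a delayed start or a restart.
4. **Add to SAP 7.6.4** the Kaplan-Meier time to first grade 3/4/5 toxicity, in the SP population, from the first everolimus dose. Date laboratory events by the test date and state the check interval beside the result. SAP 7.1.2 allows changes until the database is frozen, so this can be done even if visits are complete.

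**Cost.** Keeping 3-monthly visits adds at most 2 blood checks per patient, or 2 x 72 = 144 in all. Monthly visits add 16 per patient, at most 16 x 72 = 1,152 if everyone stays on everolimus for 24 months. The liver line formalises a check already implied. The SAP gains one descriptive analysis. Imaging is unchanged.
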